7 STATISTICAL ANALYSES

7.1 General Methods

Categorical variables will be summarized using counts and percentages of subjects falling into each category by treatment group and visit. Percentages given in these tables will be rounded and,

therefore, may not always sum to 100%. Continuous variables will be summarized by treatment group using the mean, standard deviation, median, Q1, Q3, minimum and maximum values.

SAS® version 9.4 will be used for statistical analyses, tabulations and graphical presentations.

7.2 Study Conduct

7.2.1 Relevant Protocol Deviations

Relevant protocol deviations, which could have an impact on the primary efficacy endpoint, will be identified for all subjects who are randomized and receive study medication during the treatment period. Details of relevant protocol deviations are provided in Appendix 1.

All subjects with relevant protocol deviations will be identified prior to database lock and unblinding of treatment assignment. All relevant protocol deviations will be listed and summarized by treatment group based on All Randomized and Treated Subjects.

If there are more than 10% of the study subjects with relevant protocol deviations, a Per-Protocol analysis excluding these subjects will be performed for the primary efficacy endpoint.

7.3 Study Population

Unless otherwise specified, the study population data will be presented on All Randomized and Treated Subjects by treatment group, all active treatment groups combined, and all treated subjects combined.

7.3.1 Subject Disposition

The following summary tables will be provided:

- Pre-Randomized Subject Status: subjects enrolled, randomized, not randomized, reason for being not randomized.
- Treatment Phase Subject Status: subjects completing the treatment period, not completing the treatment period, reason for not completing the treatment period, not reported (if any).
- End of Study Subject Status: subjects completing the study, not completing the study, reason for not completing the study, not reported (if any).
- The following by-subject listings will be provided:
 - Pre-randomized subject status
 - Treatment phase subject status
 - End of study subject status

7.3.2 Demographic Characteristics

The following summary table will be provided by treatment group:

- Demographic Characteristics Summary: age, gender, race, ethnicity, region, country.

The following by-subject listing will be provided:

- Demographic Characteristics: region, country, treatment group, informed consent date, birth date, age, gender, ethnicity, race.

7.3.3 Physical Measurement Summary

The following summary table will be provided by treatment group:

- Physical Measurement Summary: height (cm), weight (kg), body mass index (kg/m²).

The following by-subject listing will be provided:

- Physical Measurements: visit, date, study day, height (cm), weight (kg), BMI (kg/m²).

7.3.4 Medical History

The following summary table will be provided by treatment group:

- Medical History: history system.

The following by-subject listing will be provided:

- Medical History: history system, history details.

7.3.5 Prior and Concomitant Therapy

Prior medication is defined as any medication that is stopped prior to the first dose of study treatment; and concomitant medication is defined as any medication that is on-going at the time of the first dose or started after the first dose of study treatment. Medications will be coded using the WHO DRUG Dictionary Coding Guidelines (WHODrug Enhanced).

The following summary tables will be provided by treatment group:

- Concomitant Medication Summary: total subjects using medication, subjects by anatomic class/therapeutic class/generic name.
- Prior Medication Summary: total subjects using medication, subjects by anatomic class/therapeutic class/generic name.

The following by-subject listing will be provided:

- Prior and Concomitant Medications: start date, stop date, study day, anatomic class/therapeutic class/generic name/reported medication, total daily use, prior or concomitant.

7.4 Extent of Exposure

The exposure data will be presented on the As-Treated Analysis Population by treatment group.

7.4.1 Administration of Study Therapy

Table 7.4-1 provides the definition of parameters for administration of study therapy.

Table 7.4-1: Administration of Study Therapy: Definition of Parameters

BMS-986165	
Dosing schedule per protocol	3mg Q2D, 3mg QD, 3mg BID, 6mg BID, and 12mg QD
Total Dose	Total dose (mg) is sum of all doses administered during the study
Duration of treatment	Last dose date - Start dose date +1

The following parameters will be summarized (descriptive statistics):

- Number of doses received
- Total dose
- Duration of treatment

The following by-subject listing will be provided:

- Study Drug Administration: visit, date/day of dose, blister card number (flag if drug assigned but not taken), number of capsules per day.

7.4.2 Treatment Compliance

The CRF for this study will capture information on doses of the study medication. All subjects who skip any study drug dose will be listed. The number of subjects with missed doses (excluding missed doses due to premature discontinuation from the study) by number of missed doses will be summarized by treatment groups.

7.5 Efficacy

Unless otherwise specified, the efficacy data will be presented using the Efficacy Analysis population.

7.5.1 Primary Efficacy Analysis

The algorithm for PASI scoring is provided in Section 8.1.1. The percentage change from baseline in PASI will be calculated using the following formula:

$$[(\text{PASI Score at Day 85} - \text{Baseline})/\text{Baseline}] * 100$$

For a subject, PASI-75 is 1 if the percentage change from baseline is less than or equal to -75%, i.e., the subject has greater than or equal to 75% improvement in PASI score comparing to baseline. Otherwise, PASI-75 is 0. Missing value for PASI-75 will be imputed and the imputation method is described in Section 8.3.1.

The following analyses will be provided:

- To compare the response rates between each treatment group and placebo, the PASI-75 at Day 85 will be analyzed by two-sample Fisher's exact test or Chi-square test based on the observed counts. The odds ratio (odds in treatment group/odds in placebo) and the

difference in the response rates and their corresponding two-sided 95% confidence intervals (CIs) will be provided.

There will be no adjustment for multiplicity. All comparisons will be performed in a pre-specified hierarchical procedure starting from the highest dose arm to the lowest dose arm. If a comparison is not significant at level 0.05, all p-values in subsequent comparisons will be considered nominal.

- For the primary efficacy endpoint, the proportion of subjects with moderate to severe psoriasis experiencing a 75% improvement in PASI score at Day 85 (PASI-75), the count and percentage of subjects with PASI-75, along with the 95% asymptotic and Clopper-Pearson exact two-sided CIs, will be provided in each treatment group.
- A logistic regression model analysis will be performed to evaluate the impact of treatments on PASI-75 at Day 85, with treatment group, age, gender, weight, BMI, baseline PASI score, use of previous biologic treatment, study region, and use of previous biologic treatment-by-study region interaction as covariates, if applicable.
- A bar chart of PASI-75 response rate at Day 85 by treatment group will be provided.

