8.4.2 Efficacy Analyses

Primary Efficacy Analyses

The primary endpoint, the proportion of subjects with moderate to severe psoriasis experiencing a 75% improvement reduction in PASI score after 12 weeks, will be analyzed by two-sample Fisher's exact test or Chi-square test to compare the response rates between each treatment group and placebo. Cochran-Mantel-Haenszel Chi-square test, stratified according to previous treatment with a biologic and/or region (Japanese vs rest of world), will be performed. The odds ratio (odd in a treatment group/odd in placebo) in the response rates and its corresponding two-sided 90% confidence interval (CI) will be provided when using Fisher's exact test or

Cochran-Matell-Haenszel Chi-square test. If Chi-square test is performed, the difference in the response rates and its corresponding two-sided 90% confidence interval (CI) will be provided.

In addition, point estimate and 90% asymptotic and exact two-sided confidence intervals will be provided for the proportion of subjects in PASI-75 in each group. A logistic regression model may be performed to incorporate some of the covariates if these covariate are assumed to impact the response rates. Details of the tests and models will be given in the statistical analysis plan.

Secondary Efficacy Analyses

Similar analyses as in primary efficacy analyses will be performed to compare any two active arms.

A logistic model will be conducted to detect a positive trend between treatment groups of BMS-986165.

The response rate in PASI-50, PASI-75, PASI-90, and PASI-100 will be summarized by treatment and time and will be analyzed using a repeated measure model when applicable. The same analyses will be conducted stratified by previous biologic treatment and/or region. The proportion of subjects with a sPGA score of “0” or “1” will be analyzed similarly to the primary analyses. sPGA, and DLQI Score from psoriasis subjects will be tabulated by treatment and time; the corresponding changes from baseline and percent change from baseline will be calculated and summarized.

For continuous secondary endpoints (e.g. PASI, etc), point estimates and two-sided 90% confidence intervals for mean change from baseline within each treatment group will be provided. For binary endpoints (PASI, sPGA, etc.), point estimates of the response rate and two-sided 90% confidence intervals will be provided using normal approximation within each treatment group.

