5 SAMPLE SIZE AND POWER

The sample size calculation is driven by several considerations.

The first consideration is to compare the response rate in PASI-75, the proportion of subjects with moderate to severe psoriasis experiencing a 75% improvement in PASI score after 12 weeks, between BMS-986165 and placebo arms. With a one-sided, two-sample Fisher's exact test at significant level 0.05, a sample size of 42 per arm will provide at least 99% power to detect 50% increase in the PASI-75 response rate in an active arm (i.e., 60% response rate) compared to the placebo assuming the response rate is 10% in the placebo arm.

The second consideration is to assess the response rate in PASI-75 in active dose arms. Data from 42 treated subjects per arm will produce a two-sided 95% confidence interval (CI) with a margin of error at most 15.1% (half width) using normal approximation.

The third consideration is to compare the response rates in PASI-75 in two active arms. With a one-sided, two-sample Fisher's exact test at significant level 0.05, 42 subjects per arm will provide at least 82% power to detect at least 30% difference in the response rate in PASI-75 between any two active dose arms.

The proposed sample size is mainly driven by the third consideration. In addition, administration of BMS-986165 to 42 subjects in each active treatment group provides 34%, 88%, and 99% probability of observing at least one occurrence of any adverse event that would occur with 1%, 5%, or 10% incidence rate respectively.

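### SAP 7.5.4 names only a pooled CMH test and odds ratio for its subgroup question, while the test in SAP 7.5.1 omits the randomisation strata and states no side

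*SAP*

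**What the plan says.** **Primary test.** SAP 7.5.1 tests PASI-75 at Day 85 in each dose arm against placebo by Fisher's "exact test or Chi-square test based on the observed counts". It names no strata, count threshold, side or continuity correction. The tests form a fixed sequence from highest to lowest dose: "If a comparison is not significant at level 0.05, all p-values in subsequent comparisons will be considered nominal". Beside the tests, the "difference in the response rates and their corresponding two-sided 95% confidence intervals (CIs) will be provided". SAP 7.5.1 also lists a logistic model that includes prior biologic use, region and their interaction where applicable, but does not make it the test that drives the sequence.

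**Protocol.** Section 8.4.2 has the same alternative, Fisher's "exact test or Chi-square test to compare the response rates between each treatment group and placebo". Under the same primary heading it adds a CMH test "stratified according to previous treatment with a biologic and/or region (Japanese vs rest of world), will be performed". On intervals it says: "If Chi-square test is performed, the difference in the response rates and its corresponding two-sided 90% confidence interval (CI) will be provided". It then defers: "Details of the tests and models will be given in the statistical analysis plan".

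**Design and sizing.** SAP 2.2 stratifies randomisation by prior biologic use and region. SAP Section 5 sizes the trial "With a one-sided, two-sample" Fisher's exact test at 0.05 with 42 per arm. It states at least 99% power for 60% vs 10%, and at least 82% for a 30-point difference between two active arms, which mainly drove the sample size.

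**Subgroups.** SAP 7.5.4 sets out to investigate the impact of region and prior biologic use on the primary endpoint. The methods it names are a CMH test and a treatment-to-placebo odds ratio with a 95% CI. It names no within-level rate, within-level difference or treatment-by-factor test.

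**The concern.** The stratified test and the subgroup question appear to have changed places. CMH adjusts a single treatment comparison for strata. That is the job the protocol gave it under the primary analysis, and it suits a trial randomised by those strata. In the SAP it appears only under subgroup analyses, where the question is whether the effect differs between levels, and a pooled odds ratio does not answer that. A benefit confined to biologic-naive patients could be reported as a general one.

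The second issue is the gate of the fixed sequence. Its p-value has no stated side, and the one-sided sizing does not match the two-sided 95% intervals. In a weaker arm the side can decide whether later p-values become nominal.

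**Working it through.** **1. The plan's own power.** Inputs from SAP Section 5: n = 42 per arm, Fisher, one-sided 0.05. Exact power is the sum over all 43 × 43 outcomes (a, b) of Bin(a; 42, p_A) × Bin(b; 42, p_B), counted where p ≤ 0.05 and a > b.
- 60% vs 10%: 99.97% (stated: at least 99%).
- 30-point difference, minimum over all pairs of rates, at 65% vs 35%: 82.6% (stated: at least 82%).

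Both reproduce.

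**2. The same sum for the other readings of 7.5.1.** All figures are in favour of active, so the last column is false superiority when both rates are 10%. The 30% and 25% rates are illustrative.

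| Test at 0.05 | 60 vs 10 | 65 vs 35 | 30 vs 10 | 25 vs 10 | 10 vs 10 |
|---|---|---|---|---|---|
| Fisher, one-sided | 99.97% | 82.6% | 66.0% | 45.6% | 2.0% |
| Fisher, two-sided | 99.89% | 76.3% | 56.4% | 35.7% | 0.9% |
| Chi-square, one-sided | 99.99% | 87.8% | 76.7% | 58.1% | 5.4% |
| Chi-square, two-sided | 99.95% | 82.6% | 65.8% | 45.7% | 2.95% |

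Continuity-corrected chi-square gives 66.0% one-sided and 52.3% two-sided at 30% vs 10%. Its lowest power at 60% vs 10% is 99.88%.

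**3. If the count wording means the usual rule** (assumed: Fisher when an expected count is below 5). With equal arms the expected responders per arm are (a + b)/2, so Fisher applies when a + b ≤ 9. That happens in 1.5% of trials at 30% vs 10%, 5.8% at 25% vs 10% and 67% at 10% vs 10%. The conclusion differs from plain chi-square in 0.4% of trials (one-sided) or 0.2% (two-sided) at 30% vs 10%, and in 1.2% or 0.65% at 25% vs 10%.

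**4. What a pooled odds ratio shows.** Assumptions: placebo 10% in both levels, balanced arms, 40% prior biologic (25 naive and 17 prior-biologic patients per arm). The Mantel-Haenszel odds ratio is Σ(a·d/N) / Σ(b·c/N), with a, b active responders and non-responders, c, d placebo responders and non-responders, and N the stratum total.
- Effect confined to naive patients (60% naive, 10% prior biologic): (15 × 22.5/50 + 1.7 × 15.3/34) / (10 × 2.5/50 + 15.3 × 1.7/34) = (6.75 + 0.765) / (0.5 + 0.765) = 5.94.
- Uniform effect with the same overall rate, P = (15 + 1.7)/42 = 39.8%: P × 0.9 / ((1 − P) × 0.1) = 5.94.

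With a common placebo rate and balanced arms the two are equal by algebra, whatever the share: 9.17 at 20% prior biologic and 3.90 at 60%. In simulation at 40%, the two-sided CMH test was significant in 93.5% of trials (confined effect) and 91.3% (uniform effect).

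**5. What stratifying the primary test changes.** Simulation, 200,000 replicates per scenario, CMH without continuity correction, assumed shares of 20–60% prior biologic and 10–30% Japan:
- Power against unstratified chi-square at 30% vs 10%: −0.9 to +2.0 points one-sided, −0.8 to +2.8 two-sided.
- At 65% vs 35%, two-sided, strata of 20/14/5/3 per arm: −3.5 to +0.6 points.
- False superiority at 10%: 5.3–5.6% one-sided. The two-sided rate over both directions is 5.0–5.5%, so by symmetry about 2.5–2.75% favours active.
- With a continuity correction (strata 20/14/5/3), two-sided power at 30% vs 10% falls from 64.8–67.7% to 52.7–56.3%.

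**6. What the subgroup fix can deliver.** The 95% half-width is 1.96 × √[(p_A(1 − p_A) + p_B(1 − p_B))/m], with m patients per arm in the level.
- m = 25, 60% vs 10%: 1.96 × √(0.33/25) = 22.5 points.
- m = 17, 10% vs 10%: 1.96 × √(0.18/17) = 20.2 points.
- With a 34/8 split: 19 and 29 points.

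Simulated Breslow-Day power at 0.05 is 38.8%, 51.6% and 53.4% at prior-biologic shares of 20%, 40% and 60%, for an effect absent in one level.

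**The case against.** **The choice of test.** A reader of the table might infer that sponsor discretion between Fisher and chi-square moves power by about ten points. The documents do not support that. The words after the alternative tie the choice to the counts, and under the usual rule almost no discretion is left at these effect sizes (step 3). What stands is that no threshold is written.

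**The side.** It is less open than it looks. SAP 7.5.1 pairs the 0.05 level with 95% intervals, and the SAP document history logs the change from 90% to 95%, so two-sided is the natural reading. Section 5 is a sizing assumption. What stands is that the side is unstated, and that the stated active-vs-active power does not carry over to two-sided Fisher.

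**Strata.** An unstratified test is valid after stratified randomisation, stratifying moves power little, and the protocol's and/or wording fixes no particular stratified test. SAP 7.5.1 already has an adjusted model. A reader might infer an invalid primary analysis or a breach of the protocol; neither follows.

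**Subgroups.** CMH may be intended within each level, and table layouts are left to a Data Presentation Plan that is not among the documents. The analysis is exploratory in a phase 2 trial, and an interaction test has low power. All of this is fair, but 7.5.4 does not say that the test is run within levels, and CMH across strata is the normal use.

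**Order.** A reader might also infer that the sequence could be rearranged after unblinding. Nothing in the documents suggests that, and the arms are consistently listed in the same order, ending with 12 mg QD.

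**Conclusion.** The point holds as a repair to analysis wording, worth making before unblinding. It does not show an invalid trial.

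- **Subgroups, the most substantive part.** If CMH is run across strata, 7.5.4 cannot answer its own question: an effect confined to one level and a uniform effect share an expected odds ratio of 5.94. Exact equality rests on equal placebo rates in both levels and balanced arms. The value 5.94 also rests on the 40% share and the 60%/10% split.
- **Primary test.** The unstratified test is valid. Stratifying is an inexpensive alignment with the randomisation and with the protocol's list of primary analyses.
- **Side.** Two-sided fits the SAP's intervals. If two-sided Fisher is used between active arms, the power that drove the sample size is 76.3%, not 82%.
- **Order.** This is a minor clarification: 6 mg BID and 12 mg QD have the same total daily dose (2 × 6 = 12 mg), so highest to lowest does not rank them.

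At the planned 60% vs 10% none of the Fisher or chi-square options matters. They matter only for weaker arms.

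**What to change.** Before unblinding:

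1. **SAP 7.5.4.** Report PASI-75 rates and treatment-minus-placebo differences with 95% CIs within each region and within each level of prior biologic use. Add a treatment-by-factor interaction or Breslow-Day test, labelled exploratory and with its low power noted.
2. **SAP 7.5.1.** Make CMH stratified by prior biologic use and region, without continuity correction, the primary test. Give a Mantel-Haenszel risk difference with 95% CI. Add a sparse-stratum rule, for example pooling regions within prior-biologic level when a stratum is empty in one of the two arms. Keep Fisher as a sensitivity analysis.
3. **Side and threshold.** State the side of the 0.05 level. If two-sided Fisher is used between active arms, restate the power in SAP Section 5. If Fisher or chi-square stays primary, write the count threshold.
4. **Order.** List the five comparisons with placebo by arm name in testing order.

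**Cost.** This needs SAP text and standard output, with no change to design or data. CMH gives up Fisher's conservatism: one-sided false superiority is 5.3–5.6% in the scenarios tried, against 2.0%. Choosing two-sided lowers CMH power at 30% vs 10% from 75.6–79.9% to 64.8–69.3%. Subgroup intervals will be wide, roughly ±19 to ±29 points in the splits shown. A sponsor who prefers a conservative test could name Fisher alone, with its side. That would settle which test is used but would leave the primary test unstratified.

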7.5.2 Secondary Efficacy Analyses

7.5.2.1 PASI-75

The following analyses will be provided for PASI-75:

- The Cochran-Armitage trend test will be performed to assess a positive trend between treatment groups of BMS-986165 and proportion of subjects experiencing a 75% reduction in PASI score at Day 85.
- A repeated measures logistic regression model analysis will be performed using a generalized estimating equations (GEE) model. The model will be fitted with treatment, visit, and treatment-by-visit interaction as the fixed effects and measurements within each subject as the repeated measurements. The use of previous biologic treatment, study region, and use of previous biologic treatment-by-study region interaction will be added into the model as covariates.
- A longitudinal line plot of the response rate in PASI-75 grouped by treatment will be provided.

7.5.2.2 PASI Score

The following analyses will be provided for PASI score:

- PASI score will be presented using the descriptive statistics (n, mean, median, min, max, standard deviation, Q1, Q3) at Day 1 (baseline), Day 8, Day 15, Day 29, Day 57, Day 85, and Day 115 for each group. Point estimates at each visit and two-sided 95% CIs for mean change from baseline within each treatment group will be provided.
- A longitudinal line plot of mean change (with standard error) in PASI score from baseline grouped by treatment will be provided.
- A mixed effect model analysis with repeated measures will be performed to evaluate the impact of treatments on PASI score over time. The mixed effect model will be fitted with

treatment, visit, and treatment-by-visit interaction as the fixed effects and change from baseline measurements within each subject as the repeated measurements. The baseline value, use of previous biologic treatment, study region, and use of previous biologic treatment-by-study region interaction will be added into the model as covariates. Based on the mixed effect model, the estimate and 95% confidence interval will be calculated for the difference between each active treatment and the placebo at each specified visit.

The following by-subject listing will be provided:

- PASI: date of assessment, visit, body location, area of involvement score, induration (thickness) score, erythema (redness) score, scaling (desquamation) score, derived PASI score, change from baseline, percentage change from baseline, PASI-50, PASI-75, PASI-90, and PASI-100.

